11.2.3 Device Failures and Malfunctions

Device Quality Control. All failures, performance issues and malfunctions of the device as reported by the participants will be reported to Device company.

12 Data Analysis and Statistical Considerations

12.1 Analysis Overview

The study population will be summarized descriptively by demographics and baseline clinical values. Clinical values will include scores from all components of the EXAMINER battery as well as other neuropsychological assessment scores, vital signs, and laboratory values. We will examine the distribution of our exploratory endpoints (the EXAMINER battery and APEHQ scores) using graphs and measures of normality to ensure we have planned the appropriate analyses.

Main analyses of these scores will only include subjects with non-missing data. Reason for missing data will be reported as often as possible to better inform future studies. Sensitivity analyses will be conducted to compare baseline values of tests between subjects who were able to complete the study and those who withdrew early. Neither methods of imputation nor adjustment for multiple comparisons will be utilized as they were deemed too conservative for this feasibility study. All statistical analyses will be conducted in SAS Version 9.4 using a 0.05 level of significance unless otherwise stated.

12.2 Statistical Analysis of Primary Outcomes

To evaluate the feasibility of using the EXAMINER battery as a cognitive outcome measure in the FTD population, we will report the number and percentage of our sample who were able to complete the battery. We will also document any reasons for incomplete data. We will then describe any factors that affect implementation ease or difficulty including battery components that were more challenging for subjects with advanced FTD. Finally, we will discuss the speed and efficiency of administering the tool.

The Center for Memory & Aging's recruitment capacity will be assessed by reporting the number and percentage of subjects who were: 1. contacted for participation, 2. screened, 3. screened positive, 4. able to complete the study. We will also report the average number of visits attended by our sample and any reason for screen failure or early withdrawal.

The number of unique subjects who experienced an adverse event or serious adverse event as well as the total number of each will be reported. A brief written description of these events will be provided. Suicidality, as assessed by the C-SSRS, will be included as an adverse event.

12.3 Statistical Analysis of Exploratory Outcomes

Four summarizing scores are calculated and output using the EXAMINER battery: 1. Executive Composite Score, 2. Fluency Factor Score, 3. Cognitive Control Factor Score, and 4. Working Memory Factor Score. Five domains are assessed by the APEHQ: 1. swallowing, 2. appetite, 3. eating habits, 4. food preferences, and 5. other oral behaviors. For each of these scores, we will report the mean and standard deviation from both time points as well as calculate the pre-post change among subjects who completed the two assessments. We will utilize these values to better inform future studies about possible effect sizes and do not anticipate seeing a significant change. Therefore, no inferential statistics will be performed; we will simply describe any trends we might see.

To account for missing data, UCSF is developing a formula for a global executive score called an Item Response Theory (IRT) derived score, which our researchers will also calculate. Currently, this score formula is not yet finalized by UCSF, however, it will not require any additional information or testing by patients; we plan to include this calculation in our final analyses.

Insulin levels and basic metabolic panel values (Na, K, CO2, Cl, BUN, Creatinine, Glucose and Ca) will be summarized at each time point using means and standard deviations. Changes will be discussed descriptively.

As a sensitivity analysis, we will also descriptively compare baseline EXAMINER scores, APEHQ scores, and laboratory values between subjects who completed the study and those who withdrew early or were unable to complete the final battery.

12.4 Statement of Precision

The main purposes of this study are to assess the feasibility of using the EXAMINER battery as a cognitive outcome assessment tool and evaluate the Center for Memory & Aging's ability to recruit within the FTD population. We will consider it to be feasible if at least 80% of our sample is able to complete the battery and we are able to recruit 12 subject within our enrollment period. With a sample size of 12, we will be able to estimate an EXAMINER battery completion rate of 80% to within a 95% confidence interval of $\pm 22.6\%$. We do not except to see significant changes in the exploratory outcomes (EXAMINER, APEHQ, and laboratory values) and, therefore, have not included a power calculation for these outcomes.

13 Study Conduct Considerations

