10.2 Subject Withdrawal

Subject may withdraw from study at any time for any reason without penalty or be terminated from the study by the clinical investigator (see provisions for termination by study team.) Investigational team will document the reason(s) for withdrawal. In the event a subject chooses to withdraw from study before Visit 3, the safety procedures described in Section 7.3 will be performed ideally within 3 days following subject's decision to withdraw. For all subjects who withdraw, all final safety assessments will be collected regardless of time elapsed since previous visit. In addition to the termination visit, subjects who withdraw early will be contacted within 7 days by study staff via telephone to assess development of new and/or ongoing AEs and concomitant medications. Efforts will be made to recruit subjects to replace any withdrawals at any point so as to maintain an n=12.

Subject's participation may be terminated at the discretion of the investigator. Individuals may be withdrawn for the following reasons:

- Clinically significant adverse events
- Lost to follow-up
- Protocol violations
- Inability to tolerate study medication
- Other

11 Adverse Events (AE) and Serious Adverse Events (SAE)

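### The ±22.6% precision figure for an 80% completion rate with 12 subjects implies limits of 57.4% to 102.6%; asymmetric exact or Wilson limits should replace it

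*Combined protocol and SAP*

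**What the plan says.** Completion of the EXAMINER battery is the first primary endpoint in section 4.1. Three statements in the combined protocol and SAP govern how it is judged and reported.

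- Section 12.4 sets the rule: "We will consider it to be feasible if at least 80% of our sample is able to complete the battery", together with recruiting 12 subjects in the enrolment period.
- Section 12.4 then gives the precision: with 12 subjects the study will be able to "estimate an EXAMINER battery completion rate of 80% to within a 95% confidence interval of" ±22.6%. It names no interval method and prints no lower or upper limit.
- Section 12.2 describes the analysis: "we will report the number and percentage of our sample who were able to complete the battery". No interval is planned for the result.

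Section 10.2 also bears on the denominator: "Efforts will be made to recruit subjects to replace any withdrawals at any point so as to maintain an n=12".

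**The concern.** A symmetric ± around a proportion of 80% from 12 people suggests the normal approximation, which works poorly when the sample is small and the proportion is far from one half. The sampling distribution is skewed, the upper side is bounded at 100%, and a single ± number cannot describe both sides.

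This is the only precision figure in the plan and the only quantitative statement about what 12 subjects can show. A reader would take about 57% as the lowest completion rate compatible with an 80% result. If that limit is too high, the study appears to rule out poor completion rates that it cannot rule out. That matters because the plan intends its results to inform later studies.

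**Working it through.** **Inputs.** n = 12, rate p = 0.80, 95% confidence (all section 12.4). Section 12.1 gives a 0.05 significance level. Two-sided limits are taken from the 95% interval, so z = 1.96.

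**Step 1: reproduce the plan's figure.** Wald half-width = z√(p(1−p)/n) = 1.96 × √(0.8 × 0.2/12) = 0.2263, or 22.6 points. This matches. Common variants do not: n−1 in the denominator gives 23.6, a t quantile with 11 degrees of freedom 25.4, a continuity correction 26.8, and a one-sided 5% limit 19.0.

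**Step 2: the implied limits.** 0.800 ± 0.2263 = 57.4% to 102.6%. The document does not print these, but a ± figure has no other reading.

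**Step 3: the same case by Wilson.** The limits are [p + z²/(2n) ± z√(p(1−p)/n + z²/(4n²))] / (1 + z²/n). With p = 0.8, n = 12 and z² = 3.84:

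- centre = (0.8 + 0.160)/1.320 = 0.727
- half-width = 1.96 × √(0.01333 + 0.00667)/1.320 = 0.210
- limits = 51.7% to 93.7%, that is, −28.3 and +13.7 points around 80%

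The Wald lower limit is higher by 57.37 − 51.73 = 5.6 points.

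**Step 4: attainable results.** 80% of 12 is 9.6 subjects, which cannot occur. The counts on either side of the threshold are 9 (75.0%, fails) and 10 (83.3%, passes). Exact (Clopper-Pearson) limits come from beta quantiles: lower = Beta(0.025; x, n−x+1), upper = Beta(0.975; x+1, n−x).

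| Result | Wald | Wilson | Exact |
|---|---|---|---|
| 9/12 | 50.5% to 99.5% | 46.8% to 91.1% | 42.8% to 94.5% |
| 10/12 | 62.2% to 104.4% | 55.2% to 95.3% | 51.6% to 97.9% |
| 12/12 | 100% to 100% | – | 73.5% to 100% |

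At 10/12, the smallest count that passes, the Wald lower limit is about 7 points above Wilson and 10.7 points above exact. If all 12 complete, it collapses to zero width.

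**Step 5: actual coverage at n = 12.** For each assumed true rate, the binomial probabilities are summed over the counts (0 to 12) whose interval contains that rate.

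| True rate (assumed) | Wald | Wilson | Exact |
|---|---|---|---|
| 70% | 87.6% | 94.8% | 97.7% |
| 75% | 82.7% | 91.4% | 98.6% |
| 80% | 91.2% | 98.1% | 98.1% |
| 85% | 85.3% | 97.6% | 97.6% |

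At 80%, most of the Wald shortfall comes from the 12/12 result: its probability is 0.8¹² = 6.9%, and the collapsed interval then misses the true rate.

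**Step 6: denominator.** If withdrawn subjects are replaced and all those enrolled are counted, the denominator exceeds 12. The smallest passing counts are then 11/13, 12/14 and 12/15. Taking 15 purely as an assumption, 12/15 (80.0%) gives exact limits of 51.9% to 95.7% and Wilson limits of 54.8% to 93.0%.

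**The case against.** The strongest reply is that nothing in the trial turns on this number. The feasibility rule compares an observed percentage with 80%, the sample size is fixed at 12, and the sentence is a planning approximation for an uncontrolled feasibility study. The plan never says a Wald interval will be computed from the data, so the coverage figures describe a procedure it may not use. All of that is true, and it is why the point is minor. It does not make the stated precision right. The plan chose to quote a 95% interval, and section 12.2 offers no other. The statement in section 12.3 that no inferential statistics will be performed concerns the exploratory scores, not this endpoint.

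Two further objections stand in part.

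- **Width.** Wilson is not wider overall: it spans 42.0 points at 80%, against 45.3 for Wald, or 42.6 if Wald is cut off at 100%. The interval moves down rather than widening. Only the exact interval is wider (46.3 points at 10/12, 51.7 at 9/12). The fault is therefore the position and symmetry of the limits, not a general overstatement of precision.
- **Coverage.** Wilson does not hold 95% everywhere either; it falls to 91.4% at a true rate of 75%. Wald is lower at all four rates examined, so the ranking of the methods is unaffected.

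The 57.4% against 51.7% comparison also belongs to a result that cannot occur. Moving to attainable counts does not help the Wald figure, because its gap is larger at 10/12.

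**Conclusion.** The concern holds, as a minor point. The ±22.6% is correctly calculated but comes from a method that does not suit 12 subjects and a rate near 80%. It implies an upper limit of 102.6% and a lower limit 5.6 points above Wilson at the plan's own 80%. Its actual coverage is 82.7% to 91.2% at the four assumed true rates from 70% to 85%.

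The limits rest only on the plan's n, rate and confidence level. The coverage figures rest on the assumed true rates and on independent binomial outcomes. The sample size, the 80% rule and the feasibility decision are unaffected.

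**What to change.** In section 12.4, replace ±22.6% with asymmetric limits of one named type at the counts that can occur. Suggested text: *With 12 subjects, at least 80% means 10 or more of 12. The 95% Clopper-Pearson interval is 51.6% to 97.9% at 10/12 and 42.8% to 94.5% at 9/12.* If the team prefers Wilson, the corresponding limits are 55.2% to 95.3% and 46.8% to 91.1%. The exact interval is somewhat conservative here, so either choice is defensible if it is named and used throughout.

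State in the same place who is counted in the denominator. Restate the passing count and limits if replacement of withdrawals takes it above 12. In section 12.2, add that the completion percentage will be reported with the same type of 95% interval.

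The cost is one sentence in 12.4, one phrase in 12.2 and one option in the SAS call. The stated lower limit becomes less favourable. No extra subjects are needed, and the feasibility rule stays as it is.

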13.1 Regulatory and Ethical Considerations, Including the Informed Consent Process

The study will be conducted in accordance with GCP. Subject privacy requirements will also be observed as well as the fundamental concepts of the Declaration of Helsinki (e.g. IRB approval of the study,

obtaining informed consent from all subjects, and meeting reporting requirements). The clinical trial will be registered on the clinicaltrials.gov website.

13.2 Data Safety Monitoring Board

The DSMB will be an independent group who are not participating in the trial and have no direct affiliation with HealthPartners Center for Memory & Aging. They will serve as an advisory panel to HealthPartners Center for Memory & Aging. The DSMB will be comprised of a neurologist, statistician, and intranasal insulin researcher. An un-blinded study liaison will participate in open sessions of the DSMB and serve as a liaison to the study team. A DSMB Charter will be established prior to initiation of the study. The DSMB responsibilities include but are not limited to the following:

• Stopping the study if the rate of SAE's raises safety concerns. The details will be specified in the DSMB charter.

The DSMB will convene following the study completion of 6 subjects or earlier in the case of SAEs. During the course of the trial, the DSMB will review accumulating safety data to monitor for incidence of trends that would warrant termination of the trial. The frequency of the DSMB meetings, responsibilities, membership, and procedures will be documented in the DSMB charter.

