5.5 Study Duration

Study participation will last approximately 9 weeks, consisting of a screening visit, baseline visit, followup assessment visit and two phone call visits. Subjects will receive treatment for a period of 4 weeks. Subjects who discontinue treatment will continue follow-up measures as possible.

6 Study Population

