10.1 Subject Completion

Subjects completing all 5 study visits (including the 2 phone visits) will be considered to have completed study.

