11.2 Definition of SAE

Adverse events are classified as either serious or non-serious. A serious adverse event is any event that results in:

- Death
- Life-threatening situation
- Hospitalization or prolongation of hospitalization
- Disability or incapacitation

• Other events determined by investigator to be medically significant in which subject's well-being is jeopardized (e.g. events that have high likelihood of escalating to the point of meeting criteria outlined above)

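### The one DSMB meeting point the protocol fixes counts only completers, so withdrawals for non-serious adverse events or intolerance delay that safety look instead of counting towards it

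*Combined protocol and SAP*

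**What the plan says.** Protocol section 13.2 fixes one meeting point: "The DSMB will convene following the study completion of 6 subjects or earlier in the case of SAEs". Section 10.1 defines the counting unit: "Subjects completing all 5 study visits (including the 2 phone visits) will be considered to have completed study". The fifth visit is the phone call at week 6 (section 7.1.5).

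Section 10.2 lets the investigator end a subject's participation for reasons that include "Clinically significant adverse events" and inability to tolerate the drug. On replacement it says: "Efforts will be made to recruit subjects to replace any withdrawals at any point so as to maintain an n=12". It states no cap.

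Four other provisions bear on the point:
- Section 5.5 separates stopping drug from leaving the study: "Subjects who discontinue treatment will continue follow-up measures as possible".
- Section 11.2 gives the SAE definition a judgement limb: "Other events determined by investigator to be medically significant in which subject's well-being is jeopardized".
- Section 13.2 adds: "During the course of the trial, the DSMB will review accumulating safety data to monitor for incidence of trends that would warrant termination of the" (quote cut before its last word).
- Section 13.2 leaves the rest to a document not provided: "The frequency of the DSMB meetings, responsibilities, membership, and procedures will be documented in the DSMB charter".

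No section sets a DSMB meeting by number dosed, number withdrawn or non-serious events.

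**The concern.** Read together, sections 10.1, 10.2 and 13.2 make the named look depend on subjects who tolerated the study well enough to reach week 6. Those who did not are left out of the count. Where withdrawals are due to intolerance, the look slips furthest when the safety signal is strongest.

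The SAE clause does not close this gap. Section 7.3.3 treats glucose below 70 mg/dL as clinically significant, and section 7.3 records a clinically significant change as either an AE or an SAE. Such an episode need not be serious, and neither need a run of tolerability withdrawals.

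This matters because safety and tolerability form a primary objective (section 3.1). Section 1.2 knows of no earlier clinical investigation of intranasal insulin in FTD. After the baseline visit, dosing is at home. At stake are how many subjects are dosed before independent review and how long that review takes to arrive.

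**Working it through.** **The plan's own figure.** The documents give no derivation for the trigger of six, so there is nothing to reproduce.

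**Inputs from the documents.** Trigger: 6 completers (13.2). Completion: nominally 6 weeks after first dose (10.1 and Table 1). Withdrawals replaced towards 12 (10.2).

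**Assumptions.** These are not in the documents:
- Withdrawal probability *w* after first dose is 10%, 20% or 30%. It covers withdrawals for any reason, timed uniformly over weeks 0 to 4.
- Random (Poisson) arrivals at 1 or 2 dosed subjects per month, so λ = 12/52 = 0.231 or 24/52 = 0.462 per week.
- No SAE occurs.

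**Step 1: subjects needed for six completers.** The mean is 6/(1−w). The chance of at least one withdrawal before the sixth completer is 1−(1−w)^6.
- 10%: 6/0.9 = 6.7; chance 47%
- 20%: 6/0.8 = 7.5; chance 74%
- 30%: 6/0.7 = 8.6; chance 88%

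If the count included withdrawals, the number would always be 6.

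**Step 2: subjects already dosed at the current trigger.** Others are dosed during the six weeks before the sixth completer finishes, so the mean is 6/(1−w) + 6λ. At 20% this is 7.5 + 1.4 = 8.9 (1/month) or 7.5 + 2.8 = 10.3 (2/month). The 6λ term is ordinary accrual lag and is present with no withdrawals: 6 + 1.4 = 7.4 or 6 + 2.8 = 8.8.

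**Step 3: like-for-like comparison.** The comparator keeps the week 6 milestone and changes only the counting: six dosed subjects who have each reached week 6 or withdrawn. That comes no later than six weeks after the sixth subject's first dose. The mean delay is therefore at least [6/(1−w) − 6]/λ. At 20% this is 1.5/0.231 = 6.5 weeks or 1.5/0.462 = 3.2 weeks. Simulation (20,000 trials per cell) adds the gain from withdrawals falling before week 6. Weeks run from the start of accrual, and delays are taken before rounding.

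| w | Per month | Dosed, current | Dosed, withdrawals counted | Mean week, current | Mean week, counted | Delay (weeks) |
|---|---|---|---|---|---|---|
| 10% | 1 | 8.1 | 7.3 | 34.9 | 31.5 | 3.4 |
| 10% | 2 | 9.4 | 8.6 | 20.4 | 18.6 | 1.8 |
| 20% | 1 | 8.9 | 7.2 | 38.4 | 31.1 | 7.2 |
| 20% | 2 | 10.3 | 8.4 | 22.2 | 18.1 | 4.0 |
| 30% | 1 | 10.0 | 7.1 | 43.3 | 30.8 | 12.5 |
| 30% | 2 | 11.3 | 8.2 | 24.5 | 17.7 | 6.8 |

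**Step 4: moving the milestone to Visit 3.** This would bring the look forward by about 1.4 to 1.8 weeks more. That gain comes from the earlier milestone and is not part of the counting problem.

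**Step 5: share of all dosing.** With replacement to 12 completers, 12/(1−w) subjects are dosed in the end: 13.3, 15.0 or 17.1. The shares dosed at the current trigger are 60 to 71%, 59 to 68% and 58 to 66%. With no withdrawals they are 7.4/12 = 62% and 8.8/12 = 73%.

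**The case against.** The strongest reply is that section 13.2 is more than this one trigger. It promises review of accumulating safety data, which need not be limited to completers, and leaves meeting frequency to the charter. A reader might infer that this is the only scheduled independent review. The documents do not support that: it is the only meeting point the protocol itself fixes, and the charter may add others. The objection does not remove the flaw, because a charter that follows the protocol's sentence inherits its count.

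A reader might also infer that every adverse-event withdrawal delays the look. It does not. An SAE brings the meeting forward, the SAE definition includes investigator judgement, and a subject who only stops drug may stay in follow-up and complete. What remains is study withdrawal for a non-serious event or intolerance, which section 10.2 expressly provides for.

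A third tempting reading is that nearly all subjects will have been dosed by the look. That uses 12 as the denominator and ignores replacement. On the assumptions above the share is 58 to 71%, and no higher than with no withdrawals. Replacement does not cause the delay either. It restores the sample, while the delay comes from not counting those who left.

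Finally, the assumed rates cover withdrawals for any reason, so tolerability withdrawals account for only part of the delay. The effect is small at 10%: under one extra subject dosed. Both points stand and limit the size of the finding.

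**Conclusion.** The concern holds in a limited form. The counting rule is explicit in the text and moves the wrong way: each dosed subject lost to a non-serious event or intolerance before the sixth completion delays the fixed look by one subject.

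Attributable to the counting rule alone, with no SAE and 1 to 2 dosed subjects per month, are about 0.8 extra subjects dosed and 2 to 3 weeks at 10% withdrawal. At 20% it is about 1.7 to 1.9 subjects and 4 to 7 weeks. At 30% it is about 2.9 to 3.1 subjects and 7 to 13 weeks. The direction follows from the documents; the size rests on assumed accrual and withdrawal rates. Additional charter meetings would reduce the consequence. The point should be corrected because the remedy is cheap, but it does not show that the trial lacks safety oversight.

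**What to change.** In section 13.2 and the charter, have the DSMB convene when six dosed subjects have each either reached a named milestone (Visit 3 or the week 6 call) or withdrawn from the study. Keep the SAE trigger unchanged. Require the report to cover every dosed subject, including those still on treatment, with the reason for each withdrawal.

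The cost is one sentence in each document, with no extra subjects and no extra meeting. The downside is that an early withdrawal, including one unrelated to safety, counts in full, so some of the six may have short exposure. If Visit 3 is the milestone, some will also lack the week 6 call. Visit 3 already provides the examinations, laboratory tests and adverse event review (section 7.1.4), so the loss is small.
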